#### 11.3.4.5 Time to Resolution of Diarrhea

1) Endpoint

Days from the start of dosing to first formed stool

2) Analysis Set

**CPPS** 

3) Analysis Method

Protocol No. 341-13-002

Analysis will be performed by disease group and by dose. Calculate descriptive statistics of days from the start of dosing to first formed stool (except cases where liquid or unformed stools recurs).

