#### Secondary objectives:

- To assess the recurrence rate of CDI in patients with bacterial enteritis associated with CDI after multiple doses of OPS-2071.
- To assess the time to resolution of diarrhea in patients with bacterial enteritis associated with CDI or enteric infection after multiple doses of OPS-2071.
- To assess the improvement of clinical symptoms in patients with bacterial enteritis associated with CDI or enteric infection after multiple doses of OPS-2071.
- To assess the sensitivity to OPS-2071 of the causative pathogen strain isolated from patients with bacterial enteritis associated with CDI or enteric infection.

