#### 3.3.2.5 Time to Resolution of Diarrhea

The time from the start of dosing until the first formed stool (except in cases where liquid or unformed stools recurs) will be evaluated as time to resolution of diarrhea.

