## 3.4 Target Number of Patients

A total of 60 patients with 20 patients (10 patients each in CDI and enteric infection groups) in each dosing group

Enroll 10 patients in each dosing group of the CDI group to assess microbiological outcome. For the enteric infection group, enroll at least five patients in each dosing group to assess microbiological outcome with the sum of *Salmonella*, *Campylobacter*, and pathogenic *E. coli*. If a sufficient number of patients are not available for microbiological assessment after enrollment of 10 patients in each group, enroll more patients.

Patients available for microbiological assessment are those assessed as either "excellent," "good," or "poor" according to Table 3.3-2, which means that patients assessed as "Unknown/indeterminate" will not be included in microbiological assessment.

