#### 11.1.4 Clinical per Protocol Set

The clinical per protocol set (CPPS) comprises those patients in the FAS for whom all scheduled examinations at all specified observation time points up until the end of treatment or withdrawal have been performed.

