### 11.2 Handling of Data

Baseline values are defined as the last non-missing values at screening or before IMP administration. No imputation will be performed for missing data. If a problematic patient or data are encountered, the sponsor will decide how to handle the patient or data, with advice from the expert, as necessary.

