# 11.5 Rationale for Target Number of Patients

There will be three dosing groups of OPS-2071, ie, 100, 50, 200 mg, or 100, 200, 400 mg. For each dosing group, 10 patients in CDI group will be secured for assessing microbiological outcome. For enteric infection group, at least five patients will be secured for assessing microbiological outcome as a total of *Salmonella*, *Campylobacter*, and pathogenic *E. coli*. It is assumed that bacteria will be detected almost 100% in CDI patients, and 50% in patients with enteric infection. Based on the assumption, the target number of patients in each dosing group was selected: 10 CDI patients and 10 patients with enteric infection. The target sample sizes were selected for investigation of the safety, efficacy, and pharmacokinetics of OPS-2071 while limiting the exposure to a minimum number of patients. The target number of patients is not selected by statistical methods, but selected as an evaluable sample size.

For both the groups, the priority is to enroll patients for whom microbiological assessment is possible. If a sufficient number of patients for whom microbiological

Protocol No. 341-13-002

assessment is possible is not attained after enrolling the target number of patients (10 patients), additional patients will be enrolled.

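### Time to resolution of diarrhea is described from resolvers only, with no censoring and an ambiguous, open-ended rule for returning loose stools

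*Protocol*

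**What the plan says.** Time to resolution is a secondary objective (Protocol section 2): "To assess the time to resolution of diarrhea in patients with bacterial enteritis associated with CDI or enteric infection after multiple doses of OPS-2071".

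Section 3.3.2.5 defines the endpoint as "The time from the start of dosing until the first formed stool (except in cases where liquid or unformed stools recurs"). Section 7.2.2.5 and the synopsis repeat the definition, and 7.2.2.5 has the sponsor derive the time from the fecal properties recorded in the CRF.

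Section 11.3.4.5 sets the analysis in the CPPS, by disease group and dose: "Calculate descriptive statistics of days from the start of dosing to first formed stool (except cases where liquid or unformed stools recurs"). It states no censoring rule, no time-to-event method and no value for a patient without a qualifying stool. Section 11.2 adds: "No imputation will be performed for missing data".

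The CPPS (section 11.1.4) takes patients from the full analysis set (FAS) for whom "all scheduled examinations at all specified observation time points up until the end of treatment or withdrawal have been performed". A patient who does not resolve, or who withdraws after completing the examinations, can therefore be in the set and still have nothing to contribute to this summary.

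**The concern.** A number of days exists only for patients in whom the event was seen. Mean, median and range of those days describe the successes at each dose. The worse the dose, the more of its slow or failing patients are missing from its own summary, so differences between doses shrink.

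The patients most affected are the failures. Under section 9.2, a patient who uses or is judged to need other treatment for the infection is withdrawn, so the diary of a failing patient may cover little more than the dosing period.

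The recurrence clause adds a second problem. Take a CDI patient with a formed stool on Day 3 and one loose stool weeks later. The text could give Day 3, a much later day, or no value. Symptoms are collected for Days 24 to 37 in CDI (section 7.1.5.5) and Days 8 to 13 in enteric infection (section 7.1.6.4), and nothing says when a returning loose stool stops counting.

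The trial is meant to give exploratory information for choosing a dose. With about 10 patients per dose and disease group, losing a few non-resolvers from one dose changes the picture.

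**Working it through.** **The plan's own figure.** Section 3.4 gives "A total of 60 patients with 20 patients (10 patients each in CDI and enteric infection groups) in each dosing group". That is 3 doses × 2 disease groups × 10 = 60, which reproduces. The protocol gives no figure for resolution speed or for the share who resolve, so every rate below is an assumption.

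**Inputs**
- Windows T: 7 and 10 days (dosing periods, section 6.1); 13 and 37 days (last symptom day collected, sections 7.1.6.4 and 7.1.5.5). The protocol does not say which window applies.
- Assumed exponential resolution at L = 0.30 per day (faster dose) and 0.10 per day (slower dose). True means are 1/L = 3.3 and 10 days, ratio 3. True medians are ln 2 / L = 2.3 and 6.9 days.

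**Formulas**
- Share without a value: exp(−LT)
- Mean among resolvers: 1/L − T·exp(−LT) / (1 − exp(−LT))

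Example, T = 10:
- L = 0.30: 3.333 − 10 × 0.0498 / 0.9502 = 2.81 days
- L = 0.10: 10 − 10 × 0.3679 / 0.6321 = 4.18 days
- Ratio: 4.18 / 2.81 = 1.5

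| Window (days) | Resolver mean, faster | Resolver mean, slower | Ratio (true 3) | Dropped, faster | Dropped, slower |
|---|---|---|---|---|---|
| 7 | 2.36 | 3.09 | 1.3 | 12% | 50% |
| 10 | 2.81 | 4.18 | 1.5 | 5% | 37% |
| 13 | 3.06 | 5.13 | 1.7 | 2% | 27% |
| 37 | 3.33 | 9.06 | 2.7 | about 0% | 2.5% |

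**Doses that differ only in the share who ever resolve.** Assume 90% against 40% ever resolve, with the same speed among resolvers (exponential, median 2 days) and a 10-day window. The resolver-only mean is 2.6 days and the median 1.9 days at both doses, so nothing separates them. Keeping non-resolvers as censored, the Kaplan-Meier median for the better dose solves 0.9 × (1 − 2^(−t/2)) = 0.5, giving t = 2.3 days. For the other dose it is not reached, because only 40% ever resolve.

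**At n = 10 per dose.** This scenario was simulated with whole-day times and 40,000 replicates. The worse dose looks as fast or faster in 53% of replicates by the resolver-only mean, against 3% by a median that keeps non-resolvers as later than the window.

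**The case against.** **The recurrence clause.** A reader might infer that patients whose diarrhea returns are dropped. The text does not establish that. In the definition, the parenthesis in "until the first formed stool (except in cases where liquid or unformed stools recurs") qualifies the stool, so it can equally mean that a formed stool followed by loose stools does not count and a later one supplies the time. That patient then stays in with a longer time. Only the ambiguity and the missing time limit stand.

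**Non-resolvers.** No sentence says they are left out. A complete diary with no formed stool is not plainly missing data, and the protocol leaves details to the SAP. So exclusion is inferred, but it follows from the stated method: descriptive statistics of days need a number of days, and none is assigned. A Kaplan-Meier analysis in the SAP would change the protocol's method, and section 11.4 asks for such changes to be recorded with reasons.

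**Window.** Nothing limits the endpoint to the dosing period. If slow CDI patients are followed to Day 37, the ratio is 2.7 against 3.0 and little is lost. This stands for patients who remain in the trial; withdrawal of those needing other treatment shortens observation for failures.

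**Other tables.** Clinical response by dose (section 11.3.4.3) and the symptom summaries (section 11.3.4.6) still show failures. This stands in part: the response rate pools cure with improvement, and improvement needs only one of three criteria.

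**Weight.** The endpoint is secondary and no test is planned; on sample size, section 11.5 says "The target number of patients is not selected by statistical methods, but selected as an evaluable sample size". That limits the consequence but does not make a description based on resolvers sound.

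**Conclusion.** The point holds as a defect in a stated method. Section 11.3.4.5, read with section 11.2, describes each dose on its resolvers only, and the recurrence clause can be read two ways with no time limit.

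The bias ranges from small to severe. Under the assumed rates, a true threefold difference in mean shows as about 1.3 to 2.7, depending on how long patients are observed. It vanishes entirely if doses differ only in the share who ever resolve. A reader might conclude that an ineffective dose will look almost as fast as an effective one. The documents do not support that as a general statement: it needs failures who never resolve or who are observed for only about 7 to 10 days.

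The point deserves correction because this is a named secondary objective in a dose-ranging trial. It does not undermine the trial's other efficacy summaries.

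**What to change.** Amend sections 3.3.2.5, 7.2.2.5 and 11.3.4.5, and the matching synopsis entry.

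1. **Event.** First formed stool not followed by an unformed stool up to the end-of-treatment visit (Day 11 in CDI, Day 8 in enteric infection). In CDI, later relapse belongs to the recurrence endpoint.
2. **Report.** Number and percentage resolved by Day 4 and by end of treatment, and the Kaplan-Meier median with 95% CI, by disease group and dose.
3. **One horizon.** Censor patients without an event at their last diary day up to the end-of-treatment visit. For analysis, keep patients withdrawn for lack of effect or given other therapy as unresolved to the end of the treatment period.
4. **Analysis set.** Moving to the FAS is optional, since the CPPS already admits withdrawn patients who completed their examinations. The FAS would also keep those whose examinations were incomplete.

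The cost is a paragraph of text and no new data, because the diary already records fecal properties daily (section 7.2.2.6). The medians will be longer and may not be reached. In enteric infection, which has no recurrence endpoint, loose stools after the Day 8 visit would be visible only in the symptom records collected at follow-up 1.

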### 11.3.4.6 Improvement of Clinical Symptoms

1) Endpoints

Stool count, fecal properties, blood stool, highest body temperature, abdominal pain, nausea, vomiting

2) Analysis Set

**CPPS** 

3) Analysis Method

Analysis will be performed by disease group and by dose. Frequency distribution or descriptive statistics for each variable will be calculated at each evaluation time point according to the nature of the data (continuous or discrete).

# 11.3.4.7 Drug Sensitivity of Isolated Strain

1) Endpoint

MIC values

2) Analysis Set

C. difficile isolated/identified or the strain identified as enteric infection agents by the microbiological laboratory

3) Analysis Method

Prepare a list of kinds and number of strains of the identified causative strain. Determine MIC value of OPS-2071 for the causative strain at screening and at the end of treatment (and FU2 [Day 38] for CDI group) to prepare a list.

# 11.3.5 Pharmacokinetics Endpoints

#### 11.3.5.1 Plasma Pharmacokinetics

- 1) Endpoints
  - 1) Plasma OPS-2071 concentration
  - 2) OPS-2071 pharmacokinetic parameters ( $C_{max}$ ,  $t_{max}$  and  $C_{max}/D$ )
- 2) Analysis Set

**PKS** 

#### 3) Analysis Method

- 1) Calculation method
- Plasma concentration below lower limit of quantification (0.200 μg/L) will be considered as 0 (μg/L), and used for calculation of pharmacokinetic parameters and descriptive statistics.
- $C_{max}$ ,  $t_{max}$  and  $C_{max}/D$  will be calculated for inpatients.
- The highest concentration among all blood sampling time points will be adopted as  $C_{max}$ .
- $C_{max}/D$  will be calculated by dividing  $C_{max}$  by dose.
- $t_{max}$  will be calculated using actual time after administration.

#### 2) Statistical Analysis Method

For inpatients, calculate descriptive statistics by dose and by blood sampling time point for plasma drug concentration, and by dose for pharmacokinetic parameters.

Descriptive statistics include number of patients, arithmetic mean, standard deviation (SD), coefficient of variation, minimum, median, and maximum for plasma drug concentration, and number of patients, arithmetic mean, SD, coefficient of variation, geometric mean, minimum, median, and maximum for pharmacokinetic parameters.

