#### Primary objectives:

- To assess the safety and efficacy of oral multiple doses of OPS-2071 in patients with bacterial enteritis associated with CDI or enteric infection (caused by *Salmonella*, *Campylobacter*, or pathogenic *E. coli*)
- To assess the pharmacokinetics of multiple doses of OPS-2071 in patients with bacterial enteritis associated with CDI or enteric infection.

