#### 3.1.1 Outline of Trial Schedule

The investigator or subinvestigator will obtain written informed consent from patients, register the patients to Interactive Voice Response Services (IVRS) or Interactive Web Response Services (IWRS) to obtain patient numbers, perform screening examination within 2 days before administering IMPs, and assess patient eligibility based on the result of screening examination. Patients assessed as eligible will be allocated to dosing groups via IVRS or IWRS.

Patients in the CDI group will be treated with 50, 100, 200, or 400 mg as the daily dosages of OPS-2071 twice daily for 10 days, and patients in the enteric infection group for 7 days. For both the CDI and enteric infection groups, observation will be performed on Day 4 of dosing, and the day after the final dosing (Day 11 for the CDI group; Day 8 for the enteric infection group). Further, follow-up observation will be conducted on Day 24 and Day 38 for the CDI group and on Day 14 for the enteric infection group.

The trial period of each patient will start on the day of informed consent to the day when scheduled examinations are completed (on Day 38 for the CDI group and on Day 14 for the enteric infection group or at the end of withdrawal examination). This trial will make no distinction between inpatients and outpatients. Trial schedule is shown in Figure 3.1-2.

[figure not shown]

Figure 3.1-2 Trial Schedule

\*Performed only in CDI group

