It is demonstrated that OPS-2071  $C_{max}$  is higher by 2.21 times and  $AUC_{0-t}$  by 2.04 times in administration after taking high fat meal relative to fasting. Administration after meal is desirable for the assessment of safety and PK at higher exposure. On the other hand, patients with severe symptoms of bacterial enteritis may not be able to take meals. Thus, the IMP should be administered after a meal where possible. However, for PK assessment in a steady state, the IMP must be administered after dinner on the day before blood sampling and after breakfast on the day of blood sampling to avoid any influence on PK assessment.

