#### 7.2.3 Pharmacokinetic Evaluation

#### 7.2.3.1 Plasma Pharmacokinetics

### 1) Timing

Inpatient: 1 ( $\pm$  15 minutes), 2 ( $\pm$  15 minutes), and 4 ( $\pm$  30 minutes) hours after morning administration on Day 4

Outpatient: Once within 12 hours after morning administration but before evening administration on Day 4

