#### 11.1.5 Pharmacokinetics Analysis Set

The pharmacokinetics analysis set (PKS) comprises patients in whom plasma drug concentration was measured at least once.

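### The PK summaries cover inpatients only and group by dose alone, so outpatient concentrations have no stated use and dose can be confounded with disease

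*Protocol*

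**What the plan says.** Section 2 lists among the primary objectives: "To assess the pharmacokinetics of multiple doses of OPS-2071 in patients with bacterial enteritis associated with CDI or enteric infection". Nothing there limits the objective to inpatients. Section 3.3.3.1 names plasma concentration as an endpoint alongside Cmax, tmax and Cmax/D.

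Sampling differs by care setting. Under Section 7.2.3.1, inpatients are bled at 1, 2 and 4 hours after the Day 4 morning dose. The rule for the others is: "Outpatient: Once within 12 hours after morning administration but before evening administration on Day 4". Section 3.1.1 adds: "This trial will make no distinction between inpatients and outpatients". No expected or minimum number of inpatients is given.

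The pharmacokinetics analysis set (PKS, Section 11.1.5) "comprises patients in whom plasma drug concentration was measured at least once", so an outpatient with one measured sample is in it.

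Section 11.3.5.1 takes the PKS as its analysis set and then narrows it twice. Cmax, tmax and Cmax/D "will be calculated for inpatients". For the statistics, it says: "For inpatients, calculate descriptive statistics by dose and by blood sampling time point for plasma drug concentration, and by dose for pharmacokinetic parameters". Disease group is not mentioned.

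**The concern.** Two things look wrong in what Section 11.3.5.1 fixes.

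First, the limit to inpatients is sensible for parameters that need serial samples, but it is extended to the concentrations. Outpatients give blood for a primary objective and no stated summary uses the result.

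Second, PK is grouped by dose only, whereas the analyses that span both diseases in Sections 11.3.1, 11.3.2, 11.3.3, 11.3.4.1, 11.3.4.3, 11.3.4.5 and 11.3.4.6 are by disease group and dose. The difference matters because the dose path is chosen within each disease, so the doses need not contain the same mix of diseases. This is the first trial in patients (Section 1.2.3). Its PK tables should let a reader see exposure in each disease at each dose.

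**Working it through.** **Planned number.** Section 3.4 gives 60 patients: 3 doses x 2 diseases x 10 = 60, or 20 per dose. The figure reproduces. Section 11.5 says it was not derived statistically, and no separate number is set for PK.

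**1. How many patients the PK summaries reach.** Let s be the share of inpatients. The protocol does not give s, so a range is assumed. Patients summarised = 60 x s; sampled patients without a stated summary = 60 x (1 - s).

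| Assumed s | Summarised, total | Summarised, per dose | No stated summary |
|---|---|---|---|
| 20% | 12 | 4 | 48 |
| 50% | 30 | 10 | 30 |
| 80% | 48 | 16 | 12 |

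**2. What a dose group contains.** Under the dose escalation criteria in Section 3.1, the committee assesses 100 mg separately for CDI and for enteric infection. Provided there are no safety concerns, a verdict of effective leads to 50 and 200 mg, and a verdict of not effective leads to 200 and then 400 mg. Call the disease with the first verdict A and the other B. If the verdicts differ, the planned numbers are:

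| Dose (mg/day) | Disease A | Disease B | Total |
|---|---|---|---|
| 50 | 10 | 0 | 10 |
| 100 | 10 | 10 | 20 |
| 200 | 10 | 10 | 20 |
| 400 | 0 | 10 | 10 |

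The total is still 60. The lowest dose is then all A and the highest all B. A table by dose alone cannot separate dose from disease at either end. Section 1.2.2 reports that exposure in healthy volunteers rose less than in proportion to dose, so some fall in Cmax/D with dose is already expected. A disease difference could add to that fall or offset it without being seen. This step needs no assumption about inpatient share.

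**3. Mix when the verdicts agree.** Each dose then has 10 CDI and 10 enteric patients, but only inpatients are summarised. With inpatient shares c (CDI) and e (enteric), the CDI weight in the pooled mean is c / (c + e). The shares are assumed:

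- c = 90%, e = 10%: 9 + 1 = 10 patients, CDI weight 9/10 = 90%.
- c = 90%, e = 50%: 9 + 5 = 14 patients, CDI weight 9/14 = 64%.
- c = e = 50%: 5 + 5 = 10 patients, CDI weight 50%.

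A pooled by-dose figure may therefore describe mainly one disease, and the planned table would not show it.

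**4. Whether the data for a repair exist.** Disease group and inpatient or outpatient status are recorded (Section 7.1.3). So are the sampling time and the time of the latest dose (Section 7.2.3.1), and whether doses followed meals (Section 7.2.1.6). Nothing new has to be collected.

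**The case against.** The strongest defence of the inpatient limit is that one sample, taken anywhere in a 12-hour window, cannot give an individual Cmax or tmax, and that statistics at nominal time points need the fixed 1, 2 and 4 hour schedule. That stands for the parameters and the time-point tables. It does not explain why outpatient concentrations, an endpoint in a set that includes them, have no stated presentation against time after dose.

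On disease group, the objective does not call for separate estimates, the trial is a small phase 2a study, and safety is also summarised for the whole population. This stands in part: pooling is a weakness, not a contradiction of the objective. Safety, however, is reported both pooled and by group, whereas PK is only pooled. It is also true that the two verdicts may agree, and the confounding in step 2 then does not arise.

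Section 11 leaves detail to the SAP, and Section 11.4 mentions a pharmacokinetics analysis plan. Neither is shown, and either may add outputs. But the inpatient limit and the grouping are stated rules, and Section 11.4 requires departures from the protocol's method to be recorded with reasons.

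A reader might go further and infer that the plan admits unfed doses into the PK assessment. It does not. Taking the drug after food where possible is the general rule, but for sampling Section 6.1 says that "the IMP must be administered after dinner on the day before blood sampling and after breakfast on the day of blood sampling". An unfed dose at that point is a deviation. How often it would happen is not given, and the 2.21-fold food effect on Cmax comes from a single 600 mg dose (Section 1.2.2) after a high-fat meal (Section 6.1), so no size can be attached.

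A reader might also infer that the protocol expects damaged bowel to raise absorption. Section 6.1 raises that possibility and concludes that it is unlikely for this drug. Its comparison is with healthy adults, not between the two diseases.

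**Conclusion.** The point holds, as a cheap improvement that should be made. As written, outpatient concentrations feed no stated summary. That leaves about 48, 30 or 12 of 60 patients outside the PK statistics if 20%, 50% or 80% are inpatients; the shares are assumptions. The grouping by dose alone confounds dose with disease at 50 mg and 400 mg if the committee's verdicts on 100 mg differ between diseases. The probability of that cannot be judged from the protocol.

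It would be too strong to say that the primary PK objective goes unanswered: inpatients still give Cmax, tmax and Cmax/D. Nor do the documents show that exposure differs between the diseases. The planned tables simply could not reveal it if it did. No safety or efficacy analysis is affected.

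**What to change.** Amend Section 11.3.5.1 as follows:

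- Keep Cmax, tmax and Cmax/D for inpatients. Summarise them, and the inpatient concentrations by time point, by disease group and dose as well as pooled by dose.
- List and plot all PKS concentrations, outpatients included, against actual time after dose, by disease group and dose.
- In these outputs, flag any patient whose doses around PK sampling were not taken after the required meals, using the meal record in the CRF.

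The cost is a change of wording and a few more tables, listings and plots. The drawback is small cells: at most 10 planned patients per disease and dose, and fewer once outpatients are set aside. That is acceptable in descriptive tables, and the pooled summary remains beside them.
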